## 8.2 EXCLUSION CRITERIA

Patients will be excluded from the study if they meet **any** of the following criteria:

1. Are homicidal in the opinion of the Investigator or are at suicidal risk by any of the following criteria:
  - a. any suicide attempts within 12 months prior to Visit 1 (screening) or any suicidal intent, including a plan, within 3 months prior to Visit 1 (screening)
  - b. C-SSRS answer of “YES” on item 4 or 5 (suicidal ideation) within 3 months prior to Visit 1 (Screening)
  - c. Investigator- or computer-administered MADRS score of  $\geq 5$  on item 10 (suicidal thoughts)
  - d. by Investigator clinical evaluation
2. Have a current or previous diagnosis of OCD, PTSD, eating disorder, bipolar I or II disorder, psychotic depression, schizophrenia or other psychotic disorder.
3. Have any other current Axis I DSM-5 disorder other than MDD, which is the focus of treatment.
4. Have any other clinically significant medical condition or circumstance prior to randomization that, in the opinion of the Investigator, could affect patient safety, preclude evaluation of response, interfere with the ability to comply with study procedures, or prohibit completion of the study, such as uncontrolled diabetes mellitus, renal or hepatic impairment, coronary artery disease, evidence of significant active cardiac, respiratory, or hematologic disease, cancer with  $< 5$  year remission (basal cell carcinoma is not excluded), chronic pain, fibromyalgia or gastric bypass.
5. Have had prior seizures (other than remote history of childhood febrile seizure) or other condition that would place the patient at increased risk of seizures or is taking anticonvulsants for seizure control.
6. Have a history of serious head injury (e.g., skull fracture, cerebral contusion, or trauma resulting in prolonged unconsciousness), intracranial neoplasm or hemorrhage.
7. Have had electroconvulsive treatment, transcranial magnetic stimulation or vagal stimulation in the 6 months prior to Visit 2 (baseline).
8. Have initiated psychotherapy or have had a change in psychotherapy (such as Cognitive Behavioral Therapy) or other non-pharmacological therapies (such as acupuncture or hypnosis) within 6 weeks prior to Visit 2 (baseline) or at any time during the acute phase of the study.
9. Have a visual or physical motor impairment that could interfere with the study tasks.

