- b. Discontinuation should be considered by the Investigator after consultation with the Sponsor or its Medical Monitor designee when a patient has the following abnormal liver tests:
  - i. ALT or AST > 8 x ULN
  - ii. ALT or AST > 5 x ULN for more than 2 consecutive weeks
  - iii. ALT or AST > 3 x ULN and total bilirubin level > 2 x ULN
  - iv. ALT or AST > 3 x ULN and prothrombin time > 1.5 x ULN
  - v. ALT or AST > 3 x ULN with the appearance of fatigue, nausea, vomiting, right upper-quadrant pain or tenderness, fever, rash, and/or eosinophilia (>5%).
- c. If the patient is thought to be at risk of harm to him/herself or others at any time during the study, a further psychiatric assessment by the Investigator must be conducted. Patients must be discontinued from study participation if they:
  - i. are assessed as homicidal
  - ii. are actively suicidal (any suicidal ideation with intent or specific plan or any suicide attempt)
  - iii. are at serious suicidal risk as assessed by the C-SSRS (score of "YES" on item 4 or 5)
  - iv. score  $\geq 5$  on item 10 of either the computer- or Investigator-administered MADRS item 10.

The Investigator must assure that these patients receive the appropriate psychiatric care and follow-up.

- d. Any patient who is discontinued from investigational product due to AEs or clinically significant laboratory abnormalities will be followed until resolution or clinical stabilization.
  - e. The Investigator remains responsible for following, through an appropriate healthcare option, AEs that caused the patient to discontinue study drug.
6. Unsatisfactory Therapeutic Effect
- a. If the patient requires treatment with another therapeutic agent for MDD, discontinuation from the study will occur prior to introduction of the new agent.
7. Loss to Follow-Up
- a. For patients who are lost to follow-up, all steps performed to contact them (dates of telephone calls, registered letters, etc.) will be reported in the source documents. The Investigators are required to make at least two attempts to contact the patient for a follow-up safety visit.
8. Pregnancy
- a. Study drug treatment will be discontinued for female patients who become pregnant during study. See [section 11.3.3](#) for additional information.

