#### 11.5.6 SUICIDAL IDEATION/SUICIDALITY

Suicide-related events (behavior and/or ideation) will be assessed and evaluated at every scheduled and unscheduled visit with the administration of the C-SSRS (Posner 2009). The C-SSRS captures the occurrence, severity, and frequency of suicide-related thoughts and behaviors during the assessment period. The scale includes suggested questions to solicit the type of information needed to determine if a suicide-related thought or behavior occurred. The C-SSRS was developed by the Columbia group (Posner 2009) to prospectively categorize suicide-related events. The 'Baseline' version will be used at Visit 1 (screening) and 'Since Last Visit' will be used for all subsequent visits.

If a suicide-related event is identified at any time during the study, a thorough evaluation should be performed by a study physician and appropriate medical care should be provided. In some patients taking antidepressants, worsening of depression, suicidal events (suicidal thinking and/or behavior), or unusual changes in behavior have been reported, especially, at the beginning of the drug therapy, at the time of dose changes, or early after treatment discontinuation. It is important that patients are instructed to notify their doctor immediately if they have any distressing thoughts or feelings at any time related to harm to either self or others.

The Self-Harm Supplement Form (SHSF) captures the number of discrete events of suicidal behavior, possible suicidal behavior, and non-suicidal self-injurious behavior. This scale must be administered by the Investigator at every visit.

The Self-Harm Follow-up Form (SHFU) captures the details of each episode counted on the SHSF. These details include episode description, start and end dates, associated adverse events, severity, relationship to study drug, method, intentions, cognition, actions taken, plan, stressors, and follow-up hospital visits. The SHFU is completed at any time that the SHSF number of discrete events is  $\geq 1$ .

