## 16.6. SUICIDE IDEATION/SUICIDALITY

The assessment of suicidality is based on changes from baseline in the incidence rates of suicidal behavior and suicidal ideation as measured by the Columbia Suicide Severity Rating (C-SSRS). The post-baseline C-SSRS assesses the occurrence of suicidal behavior and suicidal ideation since the last visit. The occurrence of suicidal behavior and suicidal ideation are determined as follows.

- Suicidal behavior: having answered “yes” to at least one of the following four suicidal behavior items (Items 12, 14, 15, and 16 — actual attempt, interrupted attempt, aborted attempt, and preparatory acts or behavior, respectively) at any post-baseline evaluation;
- Suicidal ideation: having answered “yes” to at least one of the following two suicidal ideation items (Items 1 and 2—wish to be dead and non-specific active suicidal thoughts, respectively).

The number and percentage of patients who indicate suicidal behavior or suicidal ideation at any post-baseline visit will be summarized.

The number of discrete events of suicidal behavior, possible suicidal behavior, and non-suicidal self-injurious behavior will be captured in the Self-Harm Supplement Form (SHSF). The number of events will also be summarized at each visit. The details of each episode are captured on the Self-Harm Follow-up Form (SHFU). The information captured in the SHFU will be listed.

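### SAP 16.6 promises a suicidality assessment against baseline but specifies only an any-post-baseline count on C-SSRS items 1–2, with no emergent category and no count for items 4–5

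*SAP*

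**What the plan says.** SAP 16.6 opens with its basis: "The assessment of suicidality is based on changes from baseline in the incidence rates of suicidal behavior and suicidal ideation". It then defines two outcomes. Behavior is a yes on any of four behavior items. Ideation is a yes on "at least one of the following two suicidal ideation items", namely items 1 and 2. The one C-SSRS summary that follows is: "The number and percentage of patients who indicate suicidal behavior or suicidal ideation at any post-baseline visit will be summarized". The rest of the section covers the self-harm forms: SHSF event counts are summarized by visit and SHFU details are listed.

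Protocol 8.3.1 uses a different part of the scale. Under the words "Patients must be discontinued from study participation if they" it includes those who "are at serious suicidal risk as assessed by the C-SSRS", defined as a yes on item 4 or 5. Protocol 8.2, exclusion 1, also uses items 4 and 5 as an entry bar, for the 3 months before Visit 1.

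Protocol 11.5.6 has the Baseline form completed at Visit 1, while the Since Last Visit form "will be used for all subsequent visits". Table 1 of the protocol schedules the C-SSRS at every visit from screening to follow-up. Protocol 13.2.11 includes the C-SSRS among the safety assessments and has safety results presented by treatment.

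**The concern.** The first sentence of SAP 16.6 and the output it specifies do not match. A programmer who follows the section produces a post-baseline count with nothing to compare it with. The category that the protocol itself treats as serious has no row.

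This bears on the secondary safety objective. Protocol 11.5.6 notes that suicidal events have been reported with antidepressants at the start of therapy, at dose changes and early after stopping, and this design contains all three. Ongoing safety review is blinded (Protocol 11.5.7) and no DMC is planned (SAP 4.1), so the final tables are the first planned view of these data by arm. If they merge persisting with new ideation and do not separate the severe items, the C-SSRS summary cannot support a statement about emergent or serious ideation relative to placebo.

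**Working it through.** No stated figure underlies this point, so there is none to reproduce. The check is a comparison of sections followed by an illustration.

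**1. Stated basis against specified output (SAP 16.6).** The basis is change from baseline in incidence. The output is occurrence at any post-baseline visit. The text specifies no baseline incidence, shift table or rule for new or worsened ideation.

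**2. Items used.** The SAP ideation outcome uses items 1–2; the protocol's serious-risk criterion uses items 4–5. The documents do not say whether a patient with item 4 or 5 must also have answered yes to item 1 or 2. If so, that patient is merged into the item 1–2 count; if not, the patient may be absent from it. Either way there is no separate count.

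**3. Who can enter with ideation.** Exclusion 1 bars:
- attempts within 12 months, and intent or a plan within 3 months, before Visit 1;
- item 4–5 ideation within 3 months before Visit 1;
- a score of 5 or more on MADRS item 10, by either administration;
- patients judged at risk by the investigator.

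Item 1–2 ideation is not barred as such. Patients with it can be enrolled, and can answer yes again after baseline.

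**4. Size of the mixing (illustration).** The only input from the documents is about 50 patients per arm (Protocol 13.1). All rates are assumptions. Let b be the proportion with item 1–2 ideation at baseline, q the proportion of those who report it again, and e the emergent rate among the others. The planned row then has expectation

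P = b·q + (1 − b)·e.

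Take e = 5% on placebo and 15% on active, a risk ratio of 3.0, with q equal in both arms.

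| b | q | Placebo, of 50 | Active, of 50 | Risk ratio in planned row | Emergent share of active count |
|---|---|---|---|---|---|
| 20% | 60% | 8.0 | 12.0 | 1.50 | 50% |
| 20% | 80% | 10.0 | 14.0 | 1.40 | 43% |
| 40% | 60% | 13.5 | 16.5 | 1.22 | 27% |
| 40% | 80% | 17.5 | 20.5 | 1.17 | 22% |
| 60% | 60% | 19.0 | 21.0 | 1.11 | 14% |
| 60% | 80% | 25.0 | 27.0 | 1.08 | 11% |

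First row: placebo 0.2 × 0.6 + 0.8 × 0.05 = 0.16; active 0.2 × 0.6 + 0.8 × 0.15 = 0.24; ratio 1.50.

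If the drug also lowers persistence, the two effects can cancel. With b = 40%, cancellation needs a persistence difference of 0.6 × 0.10 / 0.4 = 0.15. With q = 80% on placebo and 65% on active, placebo gives 0.4 × 0.80 + 0.6 × 0.05 = 0.35 and active gives 0.4 × 0.65 + 0.6 × 0.15 = 0.35. That is 17.5 of 50 in each arm, with emergent ideation still three times as frequent on active.

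**5. The severe category.** If item 4–5 cases are nested within the item 1–2 count, a row showing 20/50 against 20/50 is compatible with 5/50 against 0/50 on items 4–5, and nothing in that row would indicate it.

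**The case against.** A reader might infer that the study report cannot show emergent or serious ideation at all. The documents do not support that:

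- Protocol 13.2.1 has eCRF data listed by treatment and patient, and SAP 3.3 declares no changes from the protocol. SAP 16.6 names a listing only for the SHFU, but that does not cancel the general rule.
- Item 4–5 withdrawals fall under the adverse event heading in Protocol 8.3.1. Discontinuation reasons are summarized by arm (SAP 9), and TEAEs leading to discontinuation are tabulated (SAP 16.1.2 and 16.1.3).
- MADRS item 10 and its change from baseline are summarized by arm and visit (SAP 15.2.3.3).
- SAP 8 refers to table shells, which are not among the documents reviewed. They may hold rows that the text does not mention.

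In about 100 patients a few cases would therefore probably be traceable. That stands, but none of these is a by-arm C-SSRS summary. Suicidality has no discontinuation reason of its own. The TEAE tables depend on an event being recorded and on its coded term. Item 10 is from a different scale and is reported descriptively: two patients of 50 rising by the full 6 points move the mean by 2 × 6 / 50 = 0.24. The range would show the maximum but not how many patients reached it.

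Three other readings also go too far. A reader might say that no baseline comparison is intended, but SAP 16.6 states one; the fault is that no output delivers it. A reader might take items 4–5 to be the only suicidality bar at entry, but exclusion 1 is much wider. A reader might argue from the standard error of the planned row, but SAP 16 plans no safety comparisons unless otherwise specified, and any such figure would rest on assumed rates.

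Finally, because exclusion 1 bars item 4–5 ideation in the 3 months before Visit 1, a post-baseline yes on those items is already largely new relative to that window. A plain count by arm would nearly suffice there; the baseline reference matters mainly for items 1–2.

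**Conclusion.** The concern holds as an inconsistency within SAP 16.6 and a missing category. The stated change-from-baseline basis has no matching output, and the items that the protocol ties to mandatory discontinuation have no specified count. Individual cases may be recoverable elsewhere, but no specified C-SSRS summary shows emergent or serious ideation by arm.

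The size cannot be fixed from the documents, which give no ideation rates. Under the assumed ranges, a true emergent risk ratio of 3.0 appears as 1.50 to 1.08, and as no difference if persistence falls enough on active. This rests on some enrolled patients having item 1–2 ideation before dosing, which the entry criteria permit but do not quantify, and on the unseen shells not already supplying the rows. The change should be made because it affects what can be concluded on the safety objective. It does not affect the primary efficacy analysis.

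**What to change.** Amend SAP 16.6, before unblinding, to tabulate by arm:

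- (a) ideation at baseline and at any post-baseline visit;
- (b) n (%) with a post-baseline yes on item 4 or 5;
- (c) treatment-emergent or worsened ideation, defined as the highest post-baseline ideation item exceeding the highest pre-dose item;
- (d) suicidal behavior, on its own row.

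State which pre-dose C-SSRS records and what recall period form the reference for (a) and (c). This has to be explicit because Visit 1 uses the Baseline form, Visit 2 uses the Since Last Visit form, and the general rule in SAP 6.2 takes the last pre-dose value. That rule would normally select Visit 2 alone. A long look-back at Visit 1 would have the opposite drawback: it could mask ideation that emerges on treatment. If (c) departs from SAP 6.2, say so.

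Also specify a listing of all C-SSRS records. The cost is one expanded descriptive table and one listing, from data already collected at every visit. No visit, assessment or clinical rule changes.

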## 16.7. PHYSICAL AND NEUROLOGICAL EXAMINATION

Listings will be generated for the physical and neurological examination data.

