Based on data from rat and rabbit reproduction toxicity studies, BTRX-246040 does not pose a significant safety hazard to a developing embryo or fetus. In rats, BTRX-246040 did not cause major malformations or effects on embryo-fetal survival. Slightly reduced fetal growth and an increase in minor fetal anomalies occurred at the maternally toxic dose of 200 mg/kg/day which corresponded to an AUC of 204485 ng.h/mL on Gestation Day 17. The Margin of Safety (MOS) for the AUC at the no-observed- adverse-effect-level (NOAEL) of 75 mg/kg/day relative to the AUC at the 40 mg in study NOAA is 69-fold and 57-fold above the expected AUC at the 80 mg dose. In rabbits, BTRX-246040 did not cause major or minor fetal anomalies or adversely affect embryo-fetal survival. A slight reduction in fetal weights occurred concurrently with significant maternal toxicity (body weight loss and reduced food consumption) at 100 mg/kg/day (AUC – 11381 ng.h/mL). The MOS for the AUC at the NOAEL of 30 mg/kg/day relative to the AUC at the 40 mg dose in study NOAA is 2.5-fold and 0.9-fold at the expected AUC at the 80 mg dose. In general toxicity studies, dose-limiting toxicity was mainly related to dose- and exposure-dependent increases in severity of central nervous system (CNS) effects in rats and dogs including ataxia, tremors (dogs only), and convulsions (dogs only). The lowest maximum drug plasma concentration (Cmax) that produced convulsions in dogs (the most sensitive preclinical species) was 2400 ng/mL (approximately 19-fold above the mean Cmax anticipated with 40 mg QD and 7-fold above the mean Cmax anticipated with 80 mg QD).

The current study will use a starting dose of 40 mg QD for which observed Cmax estimates after dosing for 14 days to healthy male patients in Study NOAA ranged from 87.9 to 183 ng/mL (mean=127 ng/mL). The exposure multiple to the lowest convulsive dose in dogs is 19-fold and the exposure multiple to 1/10th the convulsive threshold in dogs is approximately 2-fold based on the mean Cmax at 40 mg observed in Study NOAA. Since this dose was well-tolerated in two separate Phase 2 studies (n = 113 male and female patients treated with BTRX-246040) in which

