### 11.5.4 NEUROLOGICAL EXAMINATION

Neurological examination of cranial nerves, motor system, sensory, and reflexes will be conducted at screening and all subsequent study visits.

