#### 13.2.11 SAFETY ANALYSES

Safety assessments include AEs, SAEs, vital signs, weight and BMI, laboratory values, neurological exams, C-SSRS, SHSF, SHFU, and ECGs. All safety analyses will be performed on the Safety Analysis Set unless otherwise specified.

The safety/tolerability of BTRX-246040 and placebo will be compared for rates of spontaneously reported TEAEs, SAEs, AEs associated with self-harm episodes, early study discontinuations, discontinuations from BTRX-246040 or placebo, and AEs leading to discontinuation from the study or from BTRX-246040 or placebo.

Data will be pooled from all investigative sites for the analyses.

Safety results will be summarized by treatment. For categorical variables, frequencies and percentages will be reported and for continuous endpoints by visit and change from baseline summaries will be presented.

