#### 3.3. CHANGES TO ANALYSIS FROM PROTOCOL

There are no planned changes from the protocol.

---

Document: C:\Users\q718413\Documents\NEP-MDD-201\_SAP\_v1.0\_Final\_06Dec2018.docx  
 Author: [name]  
 Version Number: 1.0  
 Version Date: 06Dec2018

Template No: CS\_TP\_BS016 Revision 4  
 Effective Date: 01Apr2016  
 Reference: CS\_WI\_BS005

Copyright © 2009, 2010, 2012, 2016 Quintiles Transnational Corp. All rights reserved.  
 The contents of this document are confidential and proprietary to Quintiles Transnational Corp. Unauthorized use, disclosure or reproduction is strictly prohibited.

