### 16.4.1. ECG MARKEDLY ABNORMAL CRITERIA

Markedly abnormal quantitative ECG measurements will be identified in accordance with the following predefined markedly abnormal criteria:

- Absolute values for QT interval, QTc interval, QTcB interval and QTcF will be classified as:
  - > 450 msec
  - > 480 msec
  - > 500 msec
- Change from Baseline for QT interval, QTc interval, QTcB interval and QTcF will be classified as:
  - >30 msec increase from baseline
  - >60 msec increase from baseline

Results which meet the above criteria will be flagged in the listing.

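### The SAP plans only listings for the neurological examination, so no by-arm summary of its findings is planned beyond those reported as TEAEs, although the protocol calls for one

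*SAP*

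**What the plan says.** Protocol 13.2.11 defines the scope: "Safety assessments include AEs, SAEs, vital signs, weight and BMI, laboratory values, neurological exams, C-SSRS, SHSF, SHFU, and ECGs". It then sets the reporting rule: "Safety results will be summarized by treatment", and "For categorical variables, frequencies and percentages will be reported". The last paragraph of the synopsis's statistical methods asks for both a listing and a summary of all safety data on the Safety Analysis Set.

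Protocol 11.5.4 says that the examination covers cranial nerves, motor system, sensation and reflexes, and that it "will be conducted at screening and all subsequent study visits". Table 1 of the protocol marks it at Visits 1 to 8.

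SAP 16.7 reads, in full: "Listings will be generated for the physical and neurological examination data". SAP 3.3 reads: "There are no planned changes from the protocol".

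Two neighbouring SAP sections handle their abnormality criteria in a similar way. SAP 16.4.1 sets QT/QTc limits (above 450, 480 and 500 msec; increases above 30 and 60 msec) and concludes: "Results which meet the above criteria will be flagged in the listing". SAP 16.5.1 sets vital-sign limits and ends with the same sentence.

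**The concern.** The two documents give different instructions for the same data. The protocol asks for a summary by treatment; the SAP asks for a listing and says that it changes nothing. A programmer following the SAP will produce no table, and nothing in SAP 3.3 would prompt the study report to explain the omission.

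Listing alone is reasonable for the physical examination, which is done once, at screening. The neurological examination is repeated at every visit. It looks directly at the system in which animals showed the main dose-limiting toxicity: CNS effects in rats and dogs, with ataxia, and in dogs also tremors and convulsions (protocol section 5). Safety and tolerability is a secondary objective, and the protocol states that no PK data exist for 80 mg QD. At stake is whether the report shows, side by side for the two arms, how many patients had a normal examination at baseline and an abnormal one later.

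**Working it through.** **1. The texts side by side**

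| Question | Protocol | SAP |
|---|---|---|
| Is the neurological exam a safety assessment? | Yes, named in 13.2.11 | Has its own section, 16.7 |
| How is it reported? | Summarised by treatment; frequencies and percentages if categorical; synopsis: listed and summarised | Listed |
| Is a departure declared? | 13.2.1 requires changes of method to be described and justified in the study report | 3.3: none planned |

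The SAP states a listings-only rule that conflicts with the protocol's rule. This is more than missing detail.

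**2. How the SAP treats other safety measures**

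- Laboratory data (16.3): tables of values and change, plus shift tables against the normal range.
- C-SSRS (16.6): number and percentage with suicidal behaviour or ideation at any post-baseline visit.
- ECG (16.4): tables and boxplots of actual values and change for all quantitative parameters, QTcF included. No count by arm of patients crossing the 16.4.1 limits.
- Vital signs (16.5): the sentence promising tables and boxplots refers to ECG parameters, apparently carried over from 16.4. Read literally, no vital-sign table is promised. No count by arm is planned for the 16.5.1 limits either.
- Neurological examination (16.7): listing only.

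The ECG and vital-sign gap differs in kind. For ECG the SAP does plan by-arm summaries of the measurements, so the protocol's rule for continuous data is met. What is unused is the SAP's own set of categorical criteria.

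**3. Volume of examinations**

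The protocol plans about 100 patients, with Visits 3 to 8 after the first dose: 100 × 6 = 600 scheduled post-dose examinations if nobody drops out. The number of recorded results per examination depends on the CRF, which the documents do not show.

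**4. The protocol's exposure multiples**

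Inputs (protocol section 5): lowest convulsive Cmax in dogs 2400 ng/mL; mean Cmax 127 ng/mL observed at 40 mg QD; about 350 ng/mL anticipated at 80 mg QD.

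- 40 mg: 2400 / 127 = 18.9 (stated as 19-fold)
- 80 mg: 2400 / 350 = 6.9 (stated as 7-fold)

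Both reproduce.

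**5. What a count per arm would support**

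Take 50 patients per arm (protocol 13.1) and exact two-sided 95% intervals. With no events the upper limit is 1 − 0.025^(1/50) = 0.071. The counts below are illustrations, not predictions.

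| Patients with a new abnormality | 95% interval for the rate |
|---|---|
| 0 of 50 | 0 to 7.1% |
| 1 of 50 | 0.1 to 10.6% |
| 2 of 50 | 0.5 to 13.7% |
| 5 of 50 | 3.3 to 21.8% |

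Such a table is descriptive. It would show a sizeable imbalance between arms; it would not settle a small one.

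**The case against.** The strongest reply is that neurological signs will be reported by arm anyway. Protocol 11.3.1 counts any sign as a possible AE, and SAP 16.1.1 tabulates TEAEs by system organ class and preferred term, with severity and relationship. Tremor, ataxia or a seizure entered as an AE will appear there. A reader might infer from SAP 16.7 that the report will contain no by-arm incidence of such signs; the documents do not support that. What stands against the reply is that protocol 13.2.11 describes these TEAEs as spontaneously reported, while the examination is scheduled and systematic. No section requires every new abnormal examination finding to be entered as an AE. The AE tables therefore do not replace a summary of the examination.

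Second, a reader might infer that counts per arm could not be stated at all. That is also too strong. Appendix 1 of the SAP orders listings by randomised arm by default, so counts can be made by hand. But the SAP plans no such count and defines neither a new abnormality nor a denominator.

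Third, SAP section 8 says that the shell templates determine the tables, and the shells were not available. One of them may contain the missing table. The criticism is of the SAP text.

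Fourth, the risk background is not one-sided. Phase 1 covered multiple daily doses of 40 to 200 mg in healthy males, without neurological examination findings. At 120 mg QD the mean Cmax was 570 ng/mL, a multiple of 2400 / 570 = 4.2. Blinded monitoring during this trial includes neurological exams (protocol 11.5.7). These facts moderate the concern, but they do not remove the protocol's requirement or give a comparison by arm in patients with MDD.

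**Conclusion.** The point holds in a limited form. SAP 16.7 departs from protocol 13.2.11 and the synopsis without saying so. As the text stands, the scheduled neurological examination gets no by-arm summary beyond what investigators report as TEAEs. The SAP's QTc and vital-sign criteria likewise produce flags but no counts, alongside the planned ECG tables and a vital-sign sentence that names the wrong parameters.

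The conflict between the texts is certain. What the report will finally contain is less so, because it depends on the shells. How detailed a table can be depends on how the CRF records the examination.

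This should be corrected before unblinding. It does not touch the primary analysis, and under protocol 13.2.1 a change of this kind, if not a principal feature, can be declared and justified without an amendment.

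**What to change.** **SAP 16.7.** Keep the listing. Add a Safety Analysis Set table giving, by arm:

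- n (%) normal and abnormal at each visit;
- n (%) of patients normal at baseline with an abnormal finding at any post-baseline visit, with the denominator stated (patients normal at baseline with at least one later examination).

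Break this down by domain only if the CRF records the domains separately.

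**SAP 16.4.1 and 16.5.1.** In addition to summary tables of actual values and change, add n (%) by arm meeting each predefined criterion at any post-baseline visit. For vital signs, count the absolute, change and supine-to-standing limits separately, since 16.5.1 joins them with OR.

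**SAP 16.5.** Replace the reference to ECG parameters with vital-sign parameters.

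If the sponsor prefers listings only for the neurological examination, declare and justify that departure in SAP 3.3.

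**Cost.** SAP wording and a few table shells. The examinations are already scheduled, so no new assessment is needed, and sample size, power and alpha stay as they are. The downside is a few extra descriptive tables with sparse counts, which should be presented without tests.
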